4.2.1.1 Management of diarrhoea

Other causes for diarrhoea should always be considered and treated accordingly (e.g. viral infections, SSc related diarrhoea, bacterial overgrowth, antibiotic treatment).

Diarrhoea should be managed as early as possible after onset of first symptoms with standard anti-diarrhoeal symptomatic treatment, e.g. loperamide.

If diarrhoea persists despite optimal symptomatic treatment, treatment interruption and dose reduction of nintedanib should be considered based on the recommendations described in Table [4.2.1.1: 1](#).

If a patient is having diarrhoea prior to, or during the PK profiling in Period 1 or Period 2 then the PK profiling should be postponed, since this may affect the efficacy of both medicines Microgynon[®] and nintedanib and therefore also the PK.

Table 4.2.1.1: 1 Management of diarrhoea (considered related to nintedanib)

Description	Symptomatic Treatment ¹	Action with nintedanib
Diarrhoea with increase of <4 stools per day over baseline ² .	Initiate anti-diarrhoeal medicines at first signs of symptoms (e.g. 4 mg loperamide followed by 2 mg after each loose stool or every 2-4 hours to a maximum of 16 mg/day) until bowel movements cease for 12 hours.	Continue same nintedanib dose.
Diarrhoea with increase of 4 to 6 stools per day over baseline ² .	Initiate/continue anti-diarrhoeal medicines; If diarrhoea of this severity persists for ≥48 to 72 hours assess for dehydration and electrolyte imbalance; In addition, consider intravenous (IV) fluids and electrolyte replacement as clinically indicated.	If diarrhoea persists for ≥48 to 72 hours despite optimal symptomatic care: 1. Interrupt nintedanib until recovery ³ . 2. Reduce dose to 100 mg b.i.d. after recovery.
Diarrhoea with increase of ≥7 stools per day over baseline ² ; stool incontinence, or life threatening consequences.	Follow recommendations above. In addition, consider stool work-up to exclude infectious colitis; adequate IV fluid replacement ≥24 hours, hospitalisation as clinically indicated; consider referral to a GI specialist to rule out potential differential diagnoses.	1. Interrupt nintedanib until recovery ³ . 2. Reduce dose to 100 mg b.i.d. after recovery. In case of reoccurrence of diarrhoea of this severity despite optimal symptomatic treatment and dose reduction, treatment with nintedanib should be permanently discontinued.

Footnotes:

¹ Other causes for diarrhoea should always be considered and treated accordingly (e.g. viral infections, SSc related diarrhoea, bacterial overgrowth, antibiotic treatment). The use of loperamide should be avoided 72 hours prior to and during PK sampling days (see Table 4.2.2.1: 1), so in case his happens it is advised to postpone or interrupt the PK assessments and to repeat the PK assessments again after 10 days of nintedanib use, if possible and agreed by patient and investigator.

² Baseline defined as usual stools/day prior to start of nintedanib at Day 1 (Visit 5) of Period 2.

³ See Section 4.2.1: Maximum interruption of 4 weeks allowed, if diarrhoea is related to nintedanib. If diarrhoea is not recovered within 4 weeks, the patient must be discontinued from treatment and the trial.

4.2.1.2 Management of liver enzyme elevation

Evaluate the concomitant use of other drugs known to cause liver enzyme elevations. For a detailed guidance on how to manage liver enzyme elevations, please refer to Table [4.2.1.2: 1](#).

Table 4.2.1.2: 1: Recommendations for managing liver enzyme elevations

	AST or ALT increase to			Hepatic injury ¹ (See also Section 5.2.10.1.4)
	>1.5x to <3x ULN	≥3x to <5x ULN and no signs of hepatic injury ¹	≥5x to <8x ULN, and no signs of hepatic injury ¹	
Period 1 (before nintedanib treatment)	Discontinue from study or justify continuation ²	Discontinue from study	Discontinue from study	Discontinue from study
Period 2 (on nintedanib treatment)	Continue as planned ^{2,3}	Reduce dose or interrupt nintedanib ^{4,5}	Interrupt nintedanib ⁵	Withdraw trial medication and discontinue study
		Close observation ⁶ After 2 weeks or any time later	Close observation ⁶ After 2 weeks or any time later	CLINICAL EVALUATION OF HEPATIC-INJURY (Section 5.2.10.1.4)
	<3x ULN	≥3x ULN	<3x ULN	≥3x ULN
	Reduced: Monitor bi-weekly for at least 8 weeks Interrupted: restart at reduced dose. Monitor bi-weekly for at least 8 weeks	Permanently discontinue trial Close observation ⁶	Restart at reduced dose Monitor weekly for 4 weeks, then bi-weekly for at least 8 weeks	Permanently discontinue trial medication. Close observation ⁶

Footnotes:

- ¹ A hepatic injury is defined by the following alterations of hepatic laboratory parameters (see Section 5.2.10.1.4:
 - a) ALT and/or AST ≥8 fold ULN
 - b) ALT and/or AST ≥3 fold ULN and total bilirubin ≥ 2 fold ULN*
 - c) ALT and/or AST ≥3 fold ULN and unexplained INR > 1,5*
 - d) ALT and/or AST ≥3 fold ULN and unexplained eosinophilia (>5%)*
 - e) ALT and/or AST ≥3 fold ULN and appearance of fatigue, nausea, vomiting, right upper abdominal quadrant pain or tenderness, fever and/or rash
 (Note * within the same blood sample)
- ² Investigator to confirm in writing that continuation is justified (e.g. intermittent fluctuation of transaminases).
- ³ According to visit schedule. Consider additional control visits as adequate.
- ⁴ To reduce or interrupt nintedanib is to be decided by Investigator and is based on individual risk assessment.

- ⁵ When the safety lab reports of Visit 6 show that the liver enzymes are $\geq 3x$ ULN and $< 8x$ ULN then the following must be done: to stop the PK profiling assessments, since nintedanib has to be interrupted or dose has to be decreased which will affect the PK. However, the patient may continue the trial when liver enzymes are again $< 3x$ ULN and start or continue with reduced dose. This means that the PK profiling has to be repeated again after 10 days of continued nintedanib at lower dose (100 mg b.i.d). And the monitoring of (elevated) liver enzymes should continue for 8 weeks, so also when the patient is rolling over in Trial 1199-0225. If - after 2 weeks observation- the liver enzymes are still $\geq 3xULN$ (with interrupted or reduced dose) then the patient must be permanently discontinued from nintedanib treatment and the trial.
- ⁶ Close observation: Re-test ALT and AST, alkalinephosphatase, total bilirubin, and eosinophils within 48 to 72 hours, then after approximately 7 days, then after approximately 2 weeks by using intermediate visit lab kit.

Initial assessment of liver enzyme elevation should be performed at the investigational site. Blood samples for additional monitoring may be collected at the investigational site, primary care physician or external laboratory with specific trial lab kits and sent to the central laboratory for analysis.

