- ⁵ Echocardiography will at least be performed in patients with a history of pulmonary hypertension at Screening (time window: Visit 1 to Visit 2).
- ⁶ Self-reported outcome questionnaires must always be done by the patients in a quiet place prior to any other visit procedure. Order of questionnaires: 1. SGRQ, 2. SHAQ, 3. SCTC GIT, 4. Patient's global VAS (see Appendix [10.3](#)). The SCTC GIT will only be done in countries if the locally required language version is available.
- ⁷ Laboratory safety test at Visit 5, Day 1 should be done prior to intake of nintedanib in order to get baseline laboratory values without Microgynon[®] (past the Microgynon[®] residual effect period (REP) of 3 days) or nintedanib related effects.
- ⁸ PK sampling before intake of nintedanib in Period 2 (Visits 6-8) will be done as described in the PK overview on the following pages, which also contains detailed information about other assessments and timing of intake of meals and water.
- ⁹ In Period 2/Visit 6 Nintedanib will be administered first directly followed by Microgynon[®] and both have to be intaken within 1 minute on the PK day.

- ¹⁰ Detailed information about timing and assessments during PK days in Periods 1 and 2 can be found in the overviews on the following pages. PK sampling after Microgynon[®] intake will be done at approximate timepoints t = +30 min to +12 h (9 times), at t = +24 h and t = +48 h. During PK day in Periods 1 and 2, at t = 20 h and 4 h, administration of 240 mL of water.
- ¹¹ Pregnancy testing will only be done in women of childbearing potential: β -HCG will be performed at Visit 1 only. Urine dipstick pregnancy tests will be performed at Visits 5 and EOT and FU visit if applicable. If urine test is not acceptable to local authorities, a blood test can be also done by local laboratory if needed.

Detailed overview and order of assessments on PK days in Period 1:

Period 1, Visits 2-4				
Day	Relative. time to Microgynon® intake [h:min]	Approx. Clock Time* [h:min]	Assessment/comment	PK blood for EE and LE
Visit 2, Day -3	Pre-dose		Physical examination	
	Pre-dose		Review in/exclusion criteria	
	Pre-dose		Vital signs	
	Pre-dose		12-lead ECG	
	Pre-dose		Safety Laboratory tests (preferably after ECG)	
	Pre-dose		Adverse events	
	Pre-dose		Concomitant therapy	
	Pre-dose		Compliance check	
	-00:35	07:25		x
	-00:30	07:30	Breakfast (standardized)**	
	00:00	08:00	Microgynon® intake*	
	00:30	08:30		x
	01:00	09:00		x
	01:30	09:30		x

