3.3 SELECTION OF TRIAL POPULATION

A total of 14 patients, who completed the trial and can be analysed for both treatment periods, are needed for the purpose of the trial. It is assumed that up to approximately 24 patients may have to be enrolled by approximately 12 sites to achieve the goal that 14 patients completed the trial and have data evaluable for the PK analysis.

Sites will be experienced in the management of patient with SSc-ILD and are each expected to include approximately 2 patients. Additional sites may be initiated and 'non-productive' sites may be closed to ensure sponsor's timelines

Screening of patients for this trial is competitive, i.e. screening for the trial will stop at all sites at the same time once a sufficient number of patients has been screened. Investigators will be notified about screening completion and will then not be allowed to screen additional patients for this trial.

To be able to assess the drug-drug interaction of nintedanib with contraception in female patients as accurately as possible, certain restrictions apply: please refer to Section [4.2.2.1](#). A log of all patients enrolled into the trial (i.e. who have signed informed consent) will be maintained in the Investigator Site File (ISF) irrespective of whether they have been treated with investigational drug or not.

If a patient is enrolled in error (does not meet all inclusion criteria or meets one or more exclusion criteria on the day of enrolment), the sponsor should be contacted immediately.

Re-screening of a previously declared 'screen failed' patient is allowed, but only if the previous reason(s) for screen failure (e.g. an exclusion criterion) is resolved in the time between the previous screening and the re-screening. The re-screened patient must sign a new informed consent and will get a new unique patient number.

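### The close-observation liver retests do not require INR, leaving one of four laboratory hepatic-injury criteria uncovered; the reach is very small and the fix is cheap

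*Protocol*

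**What the plan says.** Protocol Section 4.2.1.2 (Table 4.2.1.2: 1) sets out how liver enzyme elevations are handled.

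- **Definition.** Footnote 1 gives five hepatic-injury criteria, repeated in Section 5.2.10.1.4. Criterion c sets ALT and/or AST at or above 3 "fold ULN and unexplained INR > 1,5", and its asterisk means "within the same blood sample". Any of the five moves the patient to the column for withdrawing trial medication and leaving the study. Section 5.2.10.1.4 makes the event an AESI, with an immediate stop and follow-up under the drug-induced liver injury (DILI) checklist.
- **Elevation without hepatic injury, Period 2.** At 3x to below 5x ULN, nintedanib is reduced or interrupted. Footnote 4 leaves the choice open: "To reduce or interrupt nintedanib is to be decided by Investigator and is based on individual risk assessment". At 5x to below 8x it is interrupted. Both columns then require close observation.
- **Close observation (footnote 6).** "Close observation: Re-test ALT and AST, alkalinephosphatase, total bilirubin, and eosinophils within 48 to 72 hours", then at about 7 days and about 2 weeks, using the intermediate-visit kit.
- **After observation.** Below 3x ULN, the 3x to below 5x column says: "Interrupted: restart at reduced dose. Monitor bi-weekly for at least 8 weeks". A patient already on the reduced dose is monitored. If values are still at or above 3x after 2 weeks, footnote 5 says "then the patient must be permanently discontinued from nintedanib treatment and the trial".

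INR is in the coagulation row of the routine safety panel (Table 5.2.6:1).

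**The concern.** The retest list contains bilirubin and eosinophils, the analytes that criteria b and d need beyond the transaminases. INR, which criterion c needs, is absent, and no reason is given. A site that follows footnote 6 to the letter would not learn whether c has been met during close observation, yet meeting c is a mandatory stopping rule.

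Three things could go wrong.

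(i) A patient at 3x to below 5x ULN, kept on 100 mg b.i.d., goes on dosing although c is met.

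(ii) A patient meets c at an early retest, then falls below 3x ULN and continues or restarts nintedanib instead of being withdrawn.

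(iii) The event is not recorded as an AESI and the DILI work-up is not started.

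Section 1.2.1 reports fatal drug-induced liver injury with nintedanib and a higher risk of enzyme elevation in women. Every participant here is female.

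**Working it through.** The plan states no figure on this point, so there is none to reproduce. The check compares the criteria with the retest list, looks for text that closes the gap, and then sizes it.

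**Step 1. Criteria against the footnote 6 list**

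| Criterion | Needs | Covered by the list |
|---|---|---|
| a | ALT/AST | yes |
| b | ALT/AST, total bilirubin | yes |
| c | ALT/AST, INR | no |
| d | ALT/AST, eosinophils | yes |
| e | ALT/AST, symptoms | clinical |

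Three of the four laboratory criteria are covered; adding INR makes it four of four.

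**Step 2. Does other text require INR at a retest?**

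- Section 5.2.6 allows unscheduled sampling at the investigator's discretion and asks for close monitoring without naming analytes. Its additional measures apply once hepatic-injury criteria are fulfilled, which for c presupposes an INR.
- Section 5.2.10.1.4 lists unexplained coagulopathy among the symptoms that prompt testing, but the tests it then names are ALT, AST and total bilirubin.
- Section 3.3.4.1 discontinues patients with signs of hepatic injury but orders no test.
- Section 8.7 permits documented local analysis of additional tests.

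Each permits or presupposes an INR; none requires one.

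**Step 3. Where the gap can occur.** The Flow Chart schedules safety tests at Visits 1, 2, 5, 6, EOT and FU. Visit 5 precedes dosing: "Laboratory safety test at Visit 5, Day 1 should be done prior to intake of nintedanib". That leaves Visit 6 and EOT on nintedanib, both with INR. An elevation found at EOT falls largely outside this trial's dosing. The gap therefore concerns mainly elevations found at Visit 6 or at an unscheduled test. A normal INR at Visit 6 does not settle a later retest, because c needs both values from one sample.

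**Step 4. Which retests matter for dosing.** Retests fall at day 2-3, about day 7 and about day 14. At about day 14, a value at or above 3x already means permanent discontinuation, so INR then affects only AESI recording and work-up. It can change nintedanib management at 2 of the 3 retests.

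**Step 5. Ceiling on extra doses, path (i)**, at 2 capsules of 100 mg a day until about day 14:

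- c missed at day 2-3: (14 − 3) × 2 = 22 to (14 − 2) × 2 = 24 capsules
- c missed at about day 7: (14 − 7) × 2 = 14 capsules

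This requires that dose reduction was chosen, that ALT/AST stays at 3x to below 5x, and that a, b, d and e are all unmet. In the 5x to below 8x column nintedanib is interrupted, so no doses accrue during observation. Path (ii) doses come after the fall below 3x, can arise from either column, and are not quantified.

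**Step 6. Reach.** The documents give no rates. Assume that a proportion p = 1% to 10% of patients enter close observation, and that a proportion q = 2% to 10% of those have unexplained INR above 1.5 with ALT/AST at or above 3x at a retest.

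| Quantity | n = 14 | n = 24 |
|---|---|---|
| Entering observation, n × p | 0.14 to 1.4 | 0.24 to 2.4 |
| Criterion-c cases missed, n × p × q | 0.003 to 0.14 | 0.005 to 0.24 |
| P(at least one missed), 1 − (1 − pq)^n | 0.3% to 13% | 0.5% to 21% |

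The n = 14 column uses the planned completers. The n = 24 column is an outer figure, because Section 3.3 counts enrolment from consent, not exposure: "A log of all patients enrolled into the trial (i.e. who have signed informed consent) will be maintained". All missed-case figures assume that no INR is drawn at any retest.

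**The case against.** The strongest reply is that the omission is on paper only. The retests use an intermediate-visit kit whose contents are not in the documents. Section 8.7 mentions creatinine as an intermediate measurement, and creatinine is not in footnote 6, so kit sampling is evidently not confined to that list. Both close-observation columns presuppose no hepatic injury, and an investigator may order INR at any time. Full-dose anticoagulation, an INR above 2 with prolonged PT and PTT at Visit 1, and chronic liver disease are exclusions.

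Much of this stands. A reader might infer that the retests cannot assess INR. The documents do not support that: they show only that INR is not required. A reader might also take 14 to 24 capsules as the expected excess. They are ceilings that assume the result is acted on at the moment of the draw. Samples go to the central laboratory, and each day of turnaround removes 2 capsules. Nor do extra doses arise only while ALT/AST stays at 3x to below 5x, since path (ii) adds doses outside that condition.

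What the reply does not do is make INR mandatory. Discretion is a weak basis for applying a mandatory stopping rule, particularly as Section 4.2.1.2 allows these samples to be drawn by a primary care physician or external laboratory. The exclusions at entry do not rule out new injury.

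**Conclusion.** The point holds as a low-priority safety improvement. Footnote 6 does not require INR, criterion c is the only laboratory hepatic-injury criterion that the listed analytes leave uncovered, and no visible text fills the gap. The expected number of missed cases is well below one under every assumed rate, and it is zero if the kit already carries INR and the result is reviewed. Extra dosing is nil for most patients.

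A reader might infer that the interaction estimates are at risk. They are not: no pharmacokinetic endpoint, sample size or statistical result depends on this. The conclusion about the text is firm; its practical size rests on assumed rates and on kit contents that cannot be seen.

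**What to change.** Add INR to the footnote 6 list, drawn in the same sample as ALT/AST, and confirm that the intermediate-visit kit supports it. For draws away from the site, where shipping a coagulation sample may not be practical, allow a documented local INR from the same draw; Section 8.7 already permits local analysis of additional tests. No threshold or management rule changes.

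The cost is a few mL of blood, possibly one coagulation tube per retest, and a check of the kit and off-site handling. INR is already in the trial's central-laboratory panel. If the kit includes it now, the change only aligns the text with practice.

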4.2.2 Restrictions

4.2.2.1 Restrictions regarding concomitant treatment

Medication as individually indicated per discretion of the investigator is allowed unless covered by medication restrictions in Table 4.2.2.1:1.

Please also refer to cautionary notes (Section [4.2.2.2](#)).

All concomitant or rescue therapies will be recorded (including time of intake on the days of PK sampling) on the appropriate pages of the eCRF.

Table 4.2.2.1:1. Medication restrictions and requirements

	Screening and Period 1	Period 2	After EOT*
Metoclopramide, loperamide, opioid analgetics ¹	AVOID use 72 hours prior to and during PK sampling days	AVOID use 72 hours prior to and during PK sampling days	Permitted
P-glycoprotein (P-gp) and Cytochrome P450 3A4 (CYP3A4) inhibitors			
Ketoconazol, cyclosporine A (or ciclosporin), boceprevir, clarithromycin, conivaptan, erythromycin, indinavir, itraconazole, lopinavir, mibefradil, nefazodone, nelfinavir, posaconazole, ritonavir, saquinavir, telaprevir, telithromycin, voriconazole.	NOT permitted: stop at least 7 days prior to 1 st Microgynon [®] intake	NOT permitted until last PK sampling day	Permitted

Table 4.2.2.1:1. Medication restrictions and requirements (con't)

P-gp and CYP3A4 strong inducers			
Avasimibe, carbamazepine, phenytoin, rifampin	NOT permitted: stop at least 7 days prior to 1 st Microgynon [®] intake	NOT permitted until last PK sampling day	Permitted
Products including St. John's wort	NOT permitted: stop at least 7 days prior to 1 st Microgynon [®] intake	NOT permitted until last PK sampling day	Permitted
Anticoagulant and antiplatelet therapies			
Full dose therapeutic anticoagulation ³	NOT permitted (see Section 3.3.3 exclusion criterion 9b and Section 3.3.4.1)	NOT permitted discontinuation of nintedanib is highly recommended (see Section 3.3.4.1)	Permitted
High-dose antiplatelet therapy ⁴	NOT permitted (see Section 3.3.3 exclusion criterion 9b and Section 3.3.4.1)	NOT permitted discontinuation of nintedanib is highly recommended (see Section 3.3.4.1)	Permitted
Low dose antiplatelet therapy ⁵	Permitted	Permitted	Permitted
Prophylactic low dose heparin or heparin flush ⁶	permitted	Permitted	Permitted
Immunosuppressive agents			
Mycophenolate ⁷	Not permitted 2 weeks prior Visit 2	Not permitted	Permitted
Methotrexate	Permitted if stable dose for at least 6 months prior Visit 1 (otherwise washout for 8 weeks prior Visit 1)	Stable pre-trial dose to be continued ⁷	Permitted
Azathioprine	NOT permitted 8 weeks prior Visit 1	NOT permitted ⁸	Permitted
Cyclophosphamide	NOT permitted 6 month prior Visit 1	NOT permitted ⁸	Permitted
Ciclosporine A ⁹	Not permitted at least 7 days prior to 1 st Microgynon [®] intake	NOT permitted until last PK sampling day	Permitted

Table 4.2.2.1:1. Medication restrictions and requirements (con't)

Corticosteroids			
Prednisone ≤10 mg/day or equivalent	Permitted	Permitted	Permitted
Prednisone >10 mg/day or equivalent	NOT permitted 2 weeks prior Visit 1	NOT permitted	Permitted
Hormone containing contraceptives			
Hormone containing contraceptives (including vaginal and intrauterine devices and including hormone replacement therapy), e.g. used for post-menopausal symptoms	NOT permitted within 30 days prior to first administration of Microgynon®	NOT permitted	Permitted
Other restricted medications			
Pirfenidone	NOT permitted	NOT permitted	Permitted
Nintedanib (outside of the trial)	NOT permitted	NOT permitted	Permitted
Other investigational drugs	Washout 1 month or 6 half-lives (whichever is greater) prior Visit 1	NOT permitted	Permitted

Footnotes:

- * After EOT: Permitted co-medications to be evaluated based upon whether the patient will participate in 1199-0225 with same, or other restrictions.
- ¹ These drugs may influence the motility or the absorption of drug substances in the gastrointestinal tract.
- ³ Fibrinolysis, full-dose therapeutic anticoagulation (e.g. vitamin K antagonists, direct thrombin inhibitors, heparin, hirudin)
- ⁴ E.g. acetyl salicylic acid >325 mg/day, or clopidogrel >75 mg/day, or equivalent doses of other antiplatelet therapy.
- ⁵ E.g. acetyl salicylic acid ≤ 325 mg/day, or clopidogrel ≤ 75 mg/day, or equivalent doses of other antiplatelet therapy.
- ⁶ As needed for maintenance of an indwelling intravenous device (e.g. enoxaparin 4000 IU s.c. per day).
- ⁷ Mycophenolate is not allowed because of possible drug-drug interactions with levonorgestrel. (see [Section 1.2.3](#))
- ⁸ In case of clinically significant deterioration of SSc-ILD (e.g. increase in symptoms, decline in FVC > 10% and change in mRSS relative to Visit 1, if determined during the study) which warrants the initiation or dose change of an immunosuppressive agent, it is recommended to prematurely discontinue the intake of nintedanib, and proceed to the End of Treatment Visit.
- ⁹ Ciclosporine (cyclosporine) restriction only applies for the oral formulation. Topical applications like eye drops or skin cream are allowed.

